6.3 PATIENT SETS ANALYSED

All patients who received study medication will be included in the safety analysis and in the PK analysis depending on the availability of measurement values, and on their adherence to the CTP.

The enrolled set (ENR) includes all patients who signed informed consent.

Other analysis sets are defined in Section 7.3 of the CTP. The discussion of all exceptional cases and problems and the decisions on the allocation of patients to analysis sets will be made at latest at the RPM.

Table 6.3: 1 Patient sets analysed

Class of endpoint	Patient set			
	Enrolled set (ENR)	Entered set (ES)	Treated set (TS)	PK parameter analysis set (PKS)
Important PDs	X			
Disposition	X	X	X	
Demographic/baseline characteristics	X			
Safety parameters of interest	X			
PK endpoints	X			

6.5 POOLING OF CENTRES

This section is not applicable because centre is not included in the statistical model.

6.6 HANDLING OF MISSING DATA AND OUTLIERS

The reason for withdrawal (e.g. adverse events) as recorded in the electronic Case Report Form (eCRF). will be reported.

With respect to safety evaluations, it is not planned to impute missing values.

The only exception where imputation might be necessary for safety evaluation is AE dates. Missing or incomplete AE dates are imputed according to BI standards (see 001-MCG-156_RD-01 ([3](#))).

Missing data and outliers of PK data are handled according to BI standards (see 001-MCS-36-472_RD-01) ([4](#)). Concentration data identified with NOS (no sample), NOR (no valid result), NOA (not analysed), or BLQ (below the limit of quantification) will be ignored and not replaced by zero at any time point (applies also to the lag phase).

In the non-compartmental analysis, concentration data identified with NOS, NOR, and NOA will not be considered. BLQ values in the lag phase will be set to zero. The lag phase is

defined as the period between time zero and the first time point with a concentration above the quantification limit. All other BLQ values of the profile will be ignored.

6.7 BASELINE, TIME WINDOWS AND CALCULATED VISITS

Baseline is defined as the last value prior to first administration of study drug.

Time windows are defined in Section 6.1 of the CTP. Adherence to time windows will be checked at the RPM.

7. PLANNED ANALYSIS

The format of the listings and tables will follow the BI guideline "Reporting of clinical trials and project summaries" (001-MCG-159) (9).

The individual values of all patients will be listed by patient number and visit (if visit is applicable in the respective listing). Listings will also show treatment sequence, although all patients received treatments in the same sequence. AE listings will be sorted by assigned treatment (see [Section 7.8.1](#) below for details). The listings will be contained in Appendix 16.2 of the CTR.

The following standard descriptive statistical parameters will be displayed in summary tables of continuous variables:

N	number of non-missing observations
Mean	arithmetic mean
SD	standard deviation
Min	minimum
Median	median
Max	maximum

For plasma concentrations as well as for all PK parameters, the following descriptive statistics will additionally be calculated:

CV	arithmetic coefficient of variation
gMean	geometric mean
gCV	geometric coefficient of variation

Moreover, the 10th, 25th, 75th and 90th percentiles will be also presented in Section 15.6.2 for the descriptive statistics of the PK parameters.

The data format for descriptive statistics of plasma concentrations will be identical with the data format of the respective concentrations. The descriptive statistics of PK parameters will be calculated using the individual values with the number of decimal places as provided by the evaluation program. Then the individual values as well as the descriptive statistics will be reported with three significant digits in the CTR.

Tabulations of frequencies for categorical data will include all possible categories and will display the number of observations in a category as well as the percentage (%) relative to the total number of patients. Percentages will be rounded to one decimal place. The category missing will be displayed if and only if there are actually missing values. Percentages will be based on all patients in the respective patient set whether they have non-missing values or not.

7.1 DEMOGRAPHIC AND OTHER BASELINE CHARACTERISTICS

For Saint George's Respiratory Questionnaire (SGRQ), Scleroderma Health Assessment Questionnaire (SHAQ) and Scleroderma Gastrointestinal Tract Instrument (SCTC GIT 2.0), all answers will be listed.

For all other demographic and baseline characteristics, descriptive statistics are planned.

7.2 CONCOMITANT DISEASES AND MEDICATION

Concomitant diseases will be coded according to the most recent version of the Medical Dictionary for Regulatory Activities (MedDRA). Concomitant medication will be coded according to the most recent version of the World Health Organisation – Drug Dictionary.

Only descriptive statistics are planned for this section of the CTR. All reported diseases and medications will be summarized and listed.

A medication will be considered concomitant to study drug treatment, if it

- is ongoing at the time of first administration of study drug (Microgynon® or nintedanib) or
- starts after the time of first administration of study drug (Microgynon® or nintedanib) (see also [Section 6.1](#)).

The relevance of the concomitant therapies to the evaluation of PK will be decided no later than at the RPM.

7.3 TREATMENT COMPLIANCE

Nintedanib treatment compliance [%] and the assessment of whether the patient was compliant according to the protocol (yes/no, additional specification if no), will be listed as reported by the investigator in the eCRF. A footnote will explain that, in case of a treatment interruption, the compliance could be low (e.g. less than 80%) although the patient was compliant with the protocol.

Any deviations from complete intake will be addressed in the RPM (cf. [Section 6.2](#)) and described in the CTR.

7.4 PRIMARY ENDPOINTS

Analysis of relative exposure on the basis of primary endpoints will be performed as defined in Section 7.3.1 of the CTP, based on the PKS.

The statistical model defined in the CTP is an analysis of variance (ANOVA) model on the logarithmic scale including "treatment" as fixed effect and "patient" as random effect. In addition, a sensitivity analysis will be performed, using both effects as fixed effects. For

this sensitivity analysis, a statistical SASTM raw output will be presented only (in Appendix 16.1.13.3 of the CTR).

Exclusion of PK parameters

The ADS ADPP contains column variables APEXC and APEXCO indicating inclusion/exclusion (APEXC) of a PK parameter and an analysis flag comment (APEXCO). All analyses based on the PKS are based on PK parameters with APEXC equal to “Included”, regardless of the analysis flag comment APEXCO.

Exclusion of plasma concentrations

The ADS ADPC (PK concentrations per time-point) contains column variables ACEXC and ACEXCO indicating inclusion/exclusion (ACEXC) of a plasma concentration and an analysis flag comment (ACEXCO). Exclusion of a plasma concentration depends on the analysis flag comment ACEXCO. For example, if ACEXCO is set to ‘ALL CALC’, the value will be excluded for all types of analyses based on concentrations. If ACEXCO is set to ‘DESC STATS’ the value will be excluded from descriptive evaluations per planned time point. If ACEXCO contains the addition ‘TIME VIOLATION’ or ‘TIME DEVIATION’ the value can be used for further analyses based on actual times. If ACEXCO is set to ‘HALF LIFE’ the value will be excluded from half-life calculation only; the value is included for all other analyses.

The excluded concentration itself will be listed in the tables in Section 15 of the CTR associated with an appropriate flag.

Further details are given in 001-MCS-36-472_RD-01 “Noncompartmental Pharmacokinetic / Pharmacodynamic Analyses of Clinical Studies” ([4](#)) and 001-MCS-36-472_RD-03 “Description of Analytical Transfer Files and PK/PD Data Files” ([5](#)).

7.5 SECONDARY ENDPOINTS

7.5.1 Key secondary endpoints

This section is not applicable as no key secondary endpoint has been specified in the protocol.

7.5.2 Secondary endpoints

Analysis of relative exposure on the basis of the secondary endpoint will be performed in the same way as for the primary endpoints.

See [Section 7.4](#) of this TSAP for details regarding exclusion of PK parameters and plasma concentrations.

7.6.1 Safety parameters of interest

Further safety parameters of interest will be analysed as described in Section 7.8 of this TSAP.

7.7 EXTENT OF EXPOSURE

Only descriptive statistics are planned for this section of the CTR.

7.8 SAFETY ANALYSIS

All safety analyses will be performed on TS.

7.8.1 Adverse events

AEs will be coded with the most recent version of MedDRA.

The analyses of AEs will be descriptive in nature. All analyses of AEs will be based on the number of patients with AEs and not on the number of AEs.

For analysis, multiple AE occurrence data on the electronic case report form (eCRF) will be collapsed into one event provided that all of the following applies:

- All AE attributes are identical (lower level term, intensity, action taken, therapy required, seriousness, reason for seriousness, relationship, outcome, AE of special interest (AESI))
- The occurrences were overlapping or adjacent (adjacency of two occurrences is given if the second occurrence started on the same day or on the day after the first occurrence ended)

For further details on summarisation of AE data, please refer to 'Handling and summarisation of adverse event data for clinical trial reports and integrated summaries' ([6](#)) [001-MCG-156 Version 5] and "Handling of missing and incomplete AE dates" ([3](#)) [001-MCG-156_RD-01].

The analysis of AEs will be based on the concept of treatment-emergent AEs. That means that all AEs will be assigned to the screening, treatment or follow-up phases as defined in [Section 6.1](#).

Hepatic injury and gastro-intestinal perforation are defined as protocol-specified AESIs. For details on the definition of hepatic injury see CTP Section 5.2.10.1.4.

According to ICH E3 ([8](#)), AEs classified as 'other significant' need to be reported and will include those non-serious and non-significant AEs with

- (i) 'action taken = discontinuation' or 'action taken = reduced', or
- (ii) marked haematological and other lab abnormalities or leading to significant concomitant therapy as identified by the Clinical Monitor/Investigator at a Medical Quality Review Meeting.

An overall summary of AEs will be presented. This overall summary will comprise summary statistics for the class of other significant AEs according to ICH E3 ([8](#)).

The frequency of patients with AEs will be summarised by primary system organ class and preferred term. AEs which were considered by the investigator to be drug-related will be summarised separately. Separate tables will also be provided for patients with serious AEs (SAEs), patients with AESIs and patients with other significant AEs (according to ICH E3 ([8](#))). The frequency of patients with AEs will also be summarised by worst common terminology criteria, primary system organ class and preferred term.

The system organ classes and preferred terms within system organ classes will be sorted by descending relative frequency.

In addition, the frequency of patients with AEs, SAEs and drug related AEs will be summarised by safety topic, subcategory and preferred term for the organ systems 'Hepatobiliary' and 'Liver laboratories'. Safety topics and subcategories are defined on project level and stored in PDMP in the TMF ([10](#)). The most recent version of this file will be used for the analysis.

For disclosure of AE data on ClinicalTrials.gov, the frequency of patients with non-serious AEs occurring with an incidence of greater than 5 % (in preferred terms) will be summarised by primary system organ class and preferred term. The frequency of patients with SAEs will also be summarised.

For disclosure of AE data in the European union drug regulating authorities clinical trials (EudraCT) register, the frequency of AEs, the frequency of non-serious AEs with an incidence of greater than 5 % (in preferred terms) and the frequency of SAEs will be summarised.

For support of lay summaries, the frequency of patients with drug-related SAEs will be summarised by treatment, primary system organ class and preferred term.

Details collected in the eCRF regarding bleeding AEs and AEs of diarrhoea will be listed.

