12-lead ECG	x	x								x	x	
PK diary: instruction, handout and review					x	x	x	x	x			
PK sampling pre-dose for nintedanib (trough) ⁸							x	x	x			
Dispense nintedanib + continuous (b.i.d.) intake of nintedanib					x	x	x ⁹	x	x			
PK sampling pre-dose Microgynon [®]		x					x					
Standardized meal before Microgynon [®] intake		x					x					
Administration of Microgynon [®]		x					x ⁹					
PK Sampling, after Microgynon [®] intake ¹⁰		x	x	x			x	x	x			
All AEs/SAEs/ AESIs	x	x	x	x	x	x	x	x	x	x	x	
Compliance check		x			x	x	x	x	x	x		
Concomitant therapy	x	x	x	x	x	x	x	x	x	x	x	
Completion of patient participation												x

Footnotes:

- * Screening Visit 1 may take place within Day -21 to Day -7, or earlier, depending on required washout of restricted medications prior to the 1st Microgynon[®] intake at Visit 2 (see Section [4.2.2.1](#))
Period 1/Visit 2: The 1st Microgynon[®] intake and start of pharmacokinetics (PK) profiling during Period 1 must take place at least 3 days (72 hours) prior to first intake of nintedanib (Visit 5/Day 1); results of Screening Visit 1 examinations need to be awaited prior to proceeding with Period 1. In case of clinically significant electrocardiogram (ECG) or laboratory abnormalities at Visit 1, these examinations have to be repeated at an unscheduled Visit prior to Visit 2 in order to assess if the patient is still eligible and safe to continue the trial.
- ** Period 2 starts with Visit 5/Day 1 when the patient begins with the daily intake of nintedanib. During Period 2, the nintedanib intake compliance will be checked with a Telephone Call one day prior to plan PK Visit 6.
- *** Visit 6 will take place at Day 11, but may be scheduled until Day 25 (a visit window of +14 days is allowed) and will only be conducted when the patient has had at least 10 days of continuous nintedanib intake (b.i.d) at stable dose. If the patient is not able to continuously take nintedanib (150 mg b.i.d.) for at least 10 days* then Visit 6 (and the 2nd Microgynon[®] administration and PK assessments) must be postponed until at least 10 days of continuous nintedanib on stable dose was taken by the patient (* e.g. in case of a temporary interruption or nintedanib dose reduction, additional bottles of nintedanib may have to be dispensed at Visit 6, or at an Unscheduled Visit and the V5-V6 visit window can be prolonged accordingly). The next Visits must be scheduled accordingly.

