6. GENERAL ANALYSIS DEFINITIONS

6.1 TREATMENTS

For basic study information on the treatments to be administered and selection of dose, cf. Section 4 of the CTP. All patients will undergo two treatment periods in a fixed sequence.

Each patient is planned to be treated in two subsequent treatment periods. In the first treatment period, patients will receive a single dose of Microgynon® (30 mcg ethinylestradiol and 150 mcg levonorgestrel; reference treatment, R). In the second treatment period, patients will receive a single dose of Microgynon® after continuous intake of a stable dose of nintedanib (150 mg b.i.d. or 100 mg b.i.d.) for at least 10 consecutive days (test treatment, T). Nintedanib treatment will be continued for at least 14 days to approximately 28 days in this trial. The sequence of these treatment periods is fixed and the same for all patients.

Microgynon® intake in the first treatment period will be at least 3 days before first nintedanib intake in the second treatment period.

For statistical analysis of AEs and vital signs, and for listings of safety laboratory, study phases are defined for each patient as described in [Table 6.1: 1](#) and [Table 6.1: 2](#). Note that only the date of AE onset is reported in the eCRF, but not the clock time.

Table 6.1: 1 Flow chart of analysis phases for statistical analyses of AEs and vital signs

Study analysis phase	Label	Start (included in phase)	End (excluded from phase)
Screening	Screening	Date of informed consent	Date of first administration of study drug
On-treatment microgynon	MIC	Date of administration of microgynon in Treatment Period 1 I.e., the day of administration of microgynon is included in this phase.	Day of end of REP (3 days) of microgynon: Date of administration of microgynon in Treatment Period 1 + 3 days I.e., the day of end of REP is excluded from this phase.
			OR
			Date of first administration of nintedanib in Treatment Period 2 (whichever occurs first).
Follow-up microgynon	FUP-MIC	Date of administration of microgynon in Treatment Period 1 + 3 days	Date of first administration of nintedanib in Treatment Period 2 This phase does not exist, if start \geq end.
On-treatment nintedanib loading phase	Loading NIN	Date of first administration of nintedanib in Treatment Period 2	Date of administration of microgynon in Treatment Period 2

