On-treatment nintedanib plus microgynon	NIN+MIC	Date of administration of microgynon in Treatment Period 2 I.e., the day of administration of microgynon is included in this phase.	Day of end of REP (3 days) of microgynon: Date of administration of microgynon in Treatment Period 2 + 3 days I.e., the day of end of REP of microgynon is excluded from this phase.

Table 6.1: 1 Flow chart of analysis phases for statistical analyses of AEs and vital signs (continued)

Study analysis phase	Label	Start (included in phase)	End (excluded from phase)
On-treatment nintedanib	NIN	Date of administration of microgynon in Treatment Period 2 + 3 days	Day after last contact date OR If patient is reported to continue into the 1199-0225 rollover study: Day after day of End of Treatment visit (which will be done simultaneously to End of Study visit) This phase does not exist, if start \geq end.

CTR Section 15, Appendix 16.1.13.1.8.2 and Appendix 16.1.13.1.8.3 AE displays will present results for the on-treatment phases "MIC", "Loading NIN", "NIN+MIC", and "NIN" only. Screening and FUP-MIC will not be included in this analysis. CTR Section 15 AE displays (but not Appendix 16.1.13.1.8.2 and Appendix 16.1.13.1.8.3 AE displays) will additionally present the following totals:

- "**Total NIN**", defined as the total over on-treatment phases involving nintedanib, i.e. "Loading NIN" + "NIN+MIC" + "NIN".
- "**Total on-trt**", defined as the total over all on-treatment phases, i.e., "MIC" + "Loading NIN" + "NIN+MIC" + "NIN".

CTR Appendix 16.1.13.1.8.1 displays will present results for all study analysis phases defined in [Table 6.1: 1](#) above, and will additionally present the following totals:

- "**Total NIN**", defined as the total over on-treatment phases involving nintedanib, i.e. "Loading NIN" + "NIN+MIC" + "NIN".
- "**Total**", defined as the total over all study analysis phases.

Table 6.1: 2 Flow chart of analysis phases for statistical analyses of safety laboratory

Study analysis phase	Label	Start (included in phase)	End (excluded from phase)
Screening	Screening	Date of informed consent	Date/time of first administration of study drug
On-treatment microgynon	MIC	Date/time of administration of microgynon in Treatment Period 1	Date/time of administration of microgynon in Treatment Period 1 + REP (72 h)
			OR
			Date/time of first administration of nintedanib in Treatment Period 2
			(whichever occurs first).

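### The AE displays set crude patient percentages side by side for phases of 1 to 24 or more days; Loading NIN and NIN cannot be read against the 3-day columns without time at risk.

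*SAP*

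**What the plan says.** SAP 7.8.1 fixes the unit of analysis: "All analyses of AEs will be based on the number of patients with AEs and not on the number of AEs". SAP 7 adds the denominator: "Percentages will be based on all patients in the respective patient set whether they have non-missing values or not". Which patients should form the denominator of each phase is a separate matter and is not argued here.

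SAP 6.1 puts the phases into one display: "CTR Section 15, Appendix 16.1.13.1.8.2 and Appendix 16.1.13.1.8.3 AE displays will present results for the on-treatment phases" MIC, Loading NIN, NIN+MIC and NIN. Total NIN and a total over all on-treatment phases are added in CTR Section 15.

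Table 6.1: 1 includes the start day of each phase and excludes its end day:

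- **MIC** starts on the Period 1 Microgynon day and ends at "Date of administration of microgynon in Treatment Period 1 + 3 days".
- **Loading NIN** starts on the first nintedanib day and ends on the Period 2 Microgynon day.
- **NIN+MIC** starts on the Period 2 Microgynon day and ends at "Date of administration of microgynon in Treatment Period 2 + 3 days".
- **NIN** starts where NIN+MIC ends. For roll-over patients it ends at "Day after day of End of Treatment visit (which will be done simultaneously to End of Study visit"), and for all others on the day after last contact.

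The Flow Chart footnote on Visit 6 sets the spread of Loading NIN: "Visit 6 will take place at Day 11, but may be scheduled until Day 25 (a visit window of +14 days is allowed"). The same footnote lets the window be prolonged after an interruption or dose reduction.

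SAP 7.7 summarises extent of exposure descriptively in its own section. The AE section mentions neither time at risk nor rates.

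**The concern.** The share of patients with at least one AE rises with the time over which they are observed. If one column covers 3 days and the next 10 to 24, the longer column shows more patients with AEs even when the daily risk is identical. A reader of the CTR tables could then credit to nintedanib alone an excess that comes only from a longer window. In the other direction, a one-day NIN column could look reassuring. Loading NIN and NIN also vary in length from patient to patient, and the tables do not show this.

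**Working it through.** **Inputs.** Phase boundaries come from SAP Table 6.1: 1. Visit 6 (V6) on Day 11 to Day 25, EOT at V6+3, and follow-up 7 ± 2 days after the last nintedanib dose come from the protocol Flow Chart and its footnotes. About 24 patients comes from the protocol synopsis.

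**Step 1: phase lengths (end day minus start day).**

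- MIC: (V2 + 3) − V2 = 3 days. The required gap of at least 72 hours before nintedanib means the start of nintedanib does not shorten it.
- NIN+MIC: (V6 + 3) − V6 = 3 days.
- Loading NIN: 11 − 1 = 10 days, up to 25 − 1 = 24 days. With an interruption at the maximum in protocol Table 4.2.1: 1, it is at least 28 + 10 = 38 days (4 weeks) or 56 + 10 = 66 days (8 weeks).
- NIN, roll-over with EOT at V6+3: (V6 + 4) − (V6 + 3) = 1 day.
- NIN, with follow-up: 6, 8 or 10 days if the last dose is on the EOT day, and 5, 7 or 9 days if it is the evening before.

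**Step 2: check against the plan's own figure.** SAP 6.1 gives at least 14 to about 28 days of nintedanib. For roll-over patients, Loading NIN + NIN+MIC + NIN is 10 + 3 + 1 = 14 days and 24 + 3 + 1 = 28 days. Both ends are reproduced.

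**Step 3: effect of length alone.** The documents give no AE rate, so assume one constant daily hazard h in every phase. Then P(at least one AE in L days) = 1 − exp(−hL).

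| Phase | Days | h = 0.02 | h = 0.03 |
|---|---|---|---|
| MIC, NIN+MIC | 3 | 5.8% | 8.6% |
| Loading NIN, V6 on Day 11 | 10 | 18.1% | 25.9% |
| Loading NIN, V6 on Day 25 | 24 | 38.1% | 51.3% |
| NIN, roll-over | 1 | 2.0% | 3.0% |
| NIN, follow-up, longest | 10 | 18.1% | 25.9% |

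Loading NIN divided by MIC at 10 days is 18.1/5.8 = 3.1 and 25.9/8.6 = 3.0. At 24 days it is 38.1/5.8 = 6.6 and 51.3/8.6 = 6.0. One-day NIN divided by MIC is about 0.34 to 0.35. NIN+MIC divided by MIC is 1.0.

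**Step 4: wider range for the assumption.** Set h so that 5% to 30% of patients have an AE in 3 days. Loading NIN then shows 2.3 to 3.1 times the MIC percentage at 10 days and 3.1 to 6.7 times at 24 days.

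**Step 5: what a rate must use.** Dividing the percentage by the full phase length does not remove the artefact. At h = 0.03 it gives 8.6/3 = 2.9, 25.9/10 = 2.6 and 51.3/24 = 2.1 per 100 patient-days. If each patient's days are counted only to her first AE in the phase, the expected rate is 3.0 per 100 patient-days in every column.

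**The case against.** The strongest reply is that no phase comparison is planned. SAP 7.8.1 and protocol 7.3.4 call the AE analysis descriptive and plan no test. The pair that matches reference and test treatment, MIC and NIN+MIC, has the same fixed 3-day window. Both points stand, so a reader should not infer that the Microgynon comparison without and with nintedanib is distorted, or that an analysis is invalid. They do not remove the risk of misreading: protocol 7.3.4 organises the tables by treatment at onset, and adjacent columns invite comparison. In SAP Section 4 the sponsor itself doubted the value of a descriptive laboratory comparison because of the sampling schedule.

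Three limits also stand:

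- The hazard is assumed. Early-onset AEs or a real drug effect would move the percentages too, so they are strongly influenced by phase length rather than determined by it. The figure of about 6 needs every patient at Day 25; the scheduled day is Day 11.
- Rates will be imprecise. With 24 patients, MIC holds at most 24 × 3 = 72 patient-days, or about 2 patients with an AE at h = 0.03. A one-day NIN column expects fewer than one.
- AE summarisation refers to an internal standard (001-MCG-156), and the exposure definition is in SAP 5.4.2. Neither is in the available text, so an allowance there cannot be ruled out.

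Two stronger readings are tempting but not supported. A reader might infer that NIN is enriched with patients who stopped for AEs. Yet NIN begins 3 days after the second Microgynon dose, so anyone who stops before Visit 6 never enters it. A reader might also add that contact is sparser in Loading NIN. But AEs are collected continuously and assigned by onset date, Visit 6 has a pre-dose AE check, and under-reporting there would lower the Loading NIN percentage, against the length effect.

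**Conclusion.** The concern holds as a limited point about presentation. Loading NIN and NIN percentages cannot be read against the 3-day columns, while MIC against NIN+MIC can. Under an equal daily hazard of 0.02 to 0.03, length alone makes the Loading NIN percentage about 3 times that of MIC at the scheduled Day 11 and about 6 to 6.6 times at the Day 25 limit. The phase lengths follow from the documents; the hazard is an assumption. Primary and secondary PK results are untouched. This is a worthwhile low-cost improvement and not a flaw that undermines the safety analysis.

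**What to change.** In SAP 7.8.1, for each phase column of the overall AE summary, add:

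1. the total patient-days at risk;
2. beside the raw percentage, the rate of patients with a first event per 100 patient-days, counting each patient's days to her first AE in that phase or to the end of the phase.

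Add a footnote that Loading NIN and NIN percentages are not comparable with those of the 3-day phases.

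In Table 6.1: 1, define an end of Loading NIN for patients who never receive the second Microgynon dose, for example the day after last contact. At present their phase has no end in the table, so their days at risk cannot be computed.

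If the internal AE standard or SAP 5.4.2 already supplies time at risk by phase, a cross-reference and the footnote suffice.

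The cost is a few lines of SAP text, two extra rows and one date rule; no new data are needed. The downside is that the rates assume a roughly constant hazard within a phase and will be imprecise with about 24 patients, so the raw percentages should stay. Splitting NIN by roll-over status is not worthwhile at this sample size.
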